Planned Treatment	
Early CPAP group: Participants randomized to this group will start BHP-sleep and CPAP simultaneously and continue both for 8 months. BHP-sleep consists of the sleep modules of the Canadian Consortium on Neurodegeneration in Aging's (CCNA) online Brain Health PRO platform covering sleep physiology, healthy sleep habits, and information about sleep disorders like sleep apnea. Participants will receive a study-provided auto-titrating CPAP device, with settings set by one of the study sleep medicine physicians according to current clinical practice parameters. Participants will undergo an in-person mask fitting, and then will be supported by a sleep technologist with extensive clinical experience with CPAP.
 
Later CPAP group: Participants randomized to this group will start BHP-sleep without CPAP for first 4 months, followed by BHP-sleep and CPAP simultaneously for remaining 4 months of participation.

Statistical Analysis:	
For our primary analysis, this trial will model performance on the SDMT as a function of time (baseline vs. 4 months) and study group (Early CPAP vs. Later CPAP). In secondary analyses, we will consider a series of models replacing the SDMT with our secondary cognitive endpoints.
 
We will repeat the analyses above, considering the change between baseline and 8 months. We will also conduct a mixed-effect analysis including both the 4-month and 8-month time points.
 
We will again repeat the analyses above, replacing our cognitive outcomes with a) plasma GFAP b) plasma pTau-181 and c) MRI PVS burden.
 
Finally, we will use mediation analysis to examine the extent to which the effect of CPAP on change in SDMT is mediated by specific changes in sleep physiology.

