4 STUDY DESIGN

4.1 General Design

The general design of this study is a single-blinded randomized controlled trial of 206 adults randomized into two groups:

Early CPAP group: Participants randomized to this group will start BHP-sleep and CPAP simultaneously and continue both for 8 months. BHP-sleep consists of the sleep modules of the Canadian Consortium on Neurodegeneration in Aging's (CCNA) online Brain Health PRO platform covering sleep physiology, healthy sleep habits, and information about sleep disorders like sleep apnea. Participants will receive a study-provided auto-titrating CPAP device, with settings set by one of the study sleep medicine physicians according to current clinical practice parameters. Participants will undergo an in-person mask fitting, and then will be supported by a sleep technologist with extensive clinical experience with CPAP.

Later CPAP group: Participants randomized to this group will start BHP-sleep without CPAP for first 4 months, followed by BHP-sleep and CPAP simultaneously for remaining 4 months of participation.

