6 INTERVENTIONS

6.1 Continuous positive airway pressure (CPAP)

Participants randomized to the Early CPAP group will receive a study-provided auto-tiltrating CPAP device, with settings set by one of the study sleep medicine physicians according to current clinical practice parameters (9). Participants will undergo an in-person mask fitting at their baseline study visit, and then will be supported by a sleep technologist with extensive clinical experience with CPAP who will contact participants by telephone or video call. Masks, tubing, chin straps, and other equipment necessary to optimize CPAP adherence will be provided by the study as necessary to optimize adherence, which will be tracked through participants' CPAP devices.

At the start of the 5th month, participants in the Later CPAP group will receive a study-provided auto-tiltrating CPAP device following the same protocol.

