6.2.1 Administration of BHP Intervention

Participants in both groups will register at baseline on the BHP website and obtain a personal password. Participants will need to provide a valid e-mail address and password in order to login and participate in BHP. Participants will also be asked to enter a preferred name (this can be a first name or nickname), which they will be referred to as throughout their participation in the program. Name and e-mail address will not be included in the study data set. All data from BHP will be de-identified and linked to participant study ID prior to being included in our dataset. Registration will also include viewing a brief video explaining the program.

The program content consists of 24 chapters discussing the following topics. Participants will be invited to read the content at their own pace and will be given the opportunity to discuss with research staff at scheduled check-in calls. Specific chapters are:

- 1) What is sleep?
- 2) How do we sleep?

- 3) Measuring sleep
- 4) Why do we sleep – Emotional health and well-being
- 5) Why do we sleep – Physical health
- 6) Why do we sleep – To strengthen memory
- 7) How much sleep do you need?
- 8) Dreams
- 9) Sleep changes across adulthood and factors that may disturb sleep
- 10) Insomnia
- 11) Insomnia 2
- 12) Daytime sleepiness
- 13) Sleep apnea: Definition, symptoms, causes
- 14) Sleep apnea: Treatments
- 15) Restless legs syndrome
- 16) Movements during sleep
- 17) REM sleep behavior disorder (RBD)
- 18) Disrupted sleep: when to be concerned
- 19) Sleep in Alzheimer's disease
- 20) Sleep in Parkinson's Disease
- 21) Lighting up the aging brain: the effects of light
- 22) Sleep and physical activity
- 23) Recommendations for better sleep
- 24) Sleep and sex differences

We will track adherence through metadata from the BHP platform that can be exported by the study team and includes: participant ID, date an account was created, and date specific chapters are read.

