EEG: At baseline, 16 weeks and 32 weeks, participants will undergo 3 nights of home EEG using a wearable headband (MUSE-S, Interaxon, Toronto) which will undergo automated sleep staging using a random forest based model developed by our lab based on 308 MUSE-S recordings with simultaneous in-lab PSG. To develop our own model, we divided our set of n=308 recordings with simultaneous PSG-MUSE EEG recordings randomly into n=215 training and n=93 test recordings. The MUSE-S provides four-channel EEG, triaxial accelerometer (ACC), and PPG data. After segmentation into 30-second epochs and normalization of each channel within each epoch, we extract statistical and morphological features are extracted from each epoch. EEG signals undergo bandpass filtering to isolate frequency components, enabling the extraction of power spectral density (PSD) across different frequency bands (Delta, Theta, Alpha, Beta, Gamma). Similarly, PPG data is filtered and denoised before features such as PSD, dominant frequency, heart rate variability, and respiratory rate are extracted. For sleep stage classification, a 1-D Convolutional Neural Network (CNN) architecture is employed. Ground truth labels were obtained from visual analysis of simultaneously recorded full PSG. Extracted features from MUSE EEG, accelerometer, and PPG data are fed into the model, which consists of Conv1D layers with ReLU activation, followed by MaxPooling1D layers. The hierarchical features extracted by the CNN are then flattened and passed through densely connected layers with ReLU activation. The output layer employs softmax activation to output class probabilities. The model is trained using categorical cross-entropy loss and the Adam optimizer, with a learning rate of 0.001, over 10 epochs with a batch size of 32. For sleep vs wake classification, a Decision Tree classifier is used. This classifier is configured with specific parameters controlling its complexity and generalization ability, such as with a Gini impurity criterion for splitting, limiting the maximum depth of the tree to 50, and setting minimum samples per leaf to 5 and minimum samples for splitting to 5. Post-processing involves applying majority voting on predicted sleep stages to smooth transitions and enhance the coherence of the sleep architecture. Finally, the performance of the trained models, whether binary or multiclass, is evaluated using appropriate metrics such as accuracy, sensitivity, specificity, and F1-score. Sleep metrics such as total recording time, total sleep time, sleep latency, and time spent in different sleep stages (N1, N2, N3, and REM) are calculated over all test subjects to assess the efficacy of the classification pipeline. . In the n=93 test set, we saw improved performance compared to the manufacturer provided model, correctly classifying a much larger proportion of epochs of slow wave sleep (72% vs. 56%), REM sleep (89% vs. 71%), and wake (94% vs. 71%).

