
Accelerometry The AX3 is an accelerometer used to detect movement, vibrations, and orientation changes. The AX3 will be mailed to participants and a sponsor site study team member will instruct the participant on the proper application and use of the device through videoconference. The participant will be given a copy of the instruction script, in addition to an instruction card containing contact information of research staff should they have any questions. The participant will be shown how to place the device on their non-dominant wrist by research staff, and participants will be instructed to wear the device continuously for 10 days, even when bathing or swimming. During the 10 days, participants will be asked to track their work and sleep hours in a diary. At the end of 10 days, participants will return the device to the sponsor site using a pre-paid parcel system. This procedure will be repeated at 4 months and 8 months

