APPENDIX A: SCHEDULE OF EVENTS

APPENDIX B: OVERVIEW OF STUDY SCHEDULE

Date	Venue	Staff	Activities	Compensation
Pre-Baseline	Online Form	None	Online Screening Questionnaire - STOP-BANG - presence of cognitive difficulties - collect contact information	None
Pre-Baseline	Video (1 hour)	Coordinator / RA	- informed consent - exclusion criteria: driving, non-resident of Ontario, CPAP contraindicated or unwilling to start, no study partner, shift work, Insomnia Severity Index, Cambridge-Hopkins RLS, MRI contraindications - inclusion criteria: decline in cognition from previous, Lawton-Brody IADL - cognitive screening: video MoCA, Logical Memory II - Sleep wearables: Apnealink	\$10 upon completion of home sleep assessment
Pre-Baseline	Video (1 hour)	Sleep Physician + RA	- clinical sleep assessment + information necessary to prescribe CPAP	\$50
Pre-Baseline	In-Person (overnight)	RA	- in-lab PSG	\$50 upon completion of PSG
Pre-Baseline	Video (30min)	Coordinator / RA	- discuss final determination of eligibility + randomization	None
Week 0	In-Person (2-3 hours)	Coordinator / RA	- phlebotomy - cognitive evaluation (SDMT, Trails A&B, Digit Span Forward and Backward, Letter-Number, Hopkins Verbal Learning, ADAS-Cog) - BH-PRO training - CPAP mask fitting + teaching (early CPAP group) - MRI Sleep wearables: MUSE-EEG, Actigraphy	\$50
Weeks 0-16	Video/Phone	Coordinator / RA	- Week 0 days 1, 2, 5, 7; weeks 1, 2, 3, 4, 6, 8, 10, 12, 16 (early CPAP group): calls with study staff to support CPAP	None
Week 16	In-Person (2-3 hours)	Coordinator / RA	- phlebotomy - cognitive evaluation (SDMT, Trails A&B, Digit Span Forward and Backward, Letter-Number, Hopkins Verbal Learning, ADAS-Cog) - CPAP mask fitting + teaching (later CPAP group) - MRI - Sleep wearables on CPAP: Apnealink, MUSE-EEG, Actigraphy	\$50
Weeks 16-32	Video/Phone	Coordinator / RA	- Week 16 days 1, 2, 5, 7; weeks 17, 18, 19, 20, 22, 24, 28, 32 (later CPAP group): calls with study staff to support CPAP	None
Week 32	In-Person (2-3 hours)	Coordinator / RA	- phlebotomy - cognitive evaluation (SDMT, Trails A&B, Digit Span Forward and Backward, Letter-Number, Hopkins Verbal Learning, ADAS-Cog) - Sleep wearables on CPAP: Apnealink, MUSE-EEG, Actigraphy	\$50

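### The schedule does not place the baseline home EEG and actigraphy before the Early group's first CPAP night, so baseline sleep may be treated in one arm and untreated in the other

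*Protocol*

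**What the plan says.** **Timing of the recordings.** In the Protocol's Appendix B, the only wearable in the pre-baseline rows is the Apnealink. The EEG headband and actigraphy enter in the Week 0 row: "CPAP mask fitting + teaching (early CPAP group) - MRI Sleep wearables: MUSE-EEG, Actigraphy". Section 7.2.5 gives their length. For the EEG: "At baseline, 16 weeks and 32 weeks, participants will undergo 3 nights of home EEG using a wearable headband". For the accelerometer: "participants will be instructed to wear the device continuously for 10 days". It is delivered remotely: "The AX3 will be mailed to participants", with instruction by videoconference, but no mailing date is given relative to Week 0.

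**Timing of CPAP in the Early arm.** Section 6.1: "Participants will undergo an in-person mask fitting at their baseline study visit". Section 4.1: "Participants randomized to this group will start BHP-sleep and CPAP simultaneously and continue both for 8 months". Section 6.2.1 dates the education component: "Participants in both groups will register at baseline on the BHP website". Appendix B adds support calls for the Early group from day 1 of Week 0. Randomization has already taken place at the last pre-baseline video call.

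**Use of the data.** Secondary objective 4 (section 3.2) looks for sleep features that mediate the CPAP effect on cognition. The Protocol Summary describes the effect on SDMT change as "mediated by specific changes in sleep physiology". Section 9.4 makes slow-wave sleep percentage the primary mediator and calls the mediation analysis exploratory. Section 4.3 takes sleep staging from the headband and sleep fragmentation from the accelerometer.

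**The concern.** A recording of 3 or 10 nights at home cannot be completed within a 2-3 hour visit. If the devices go on at the Week 0 visit, as the row reads, an Early participant makes the baseline recording during the first nights with CPAP, while a Later participant makes it untreated.

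The two arms' baselines would then measure different things. Any early CPAP effect on sleep would sit inside the Early arm's baseline and be subtracted from its change. The between-arm contrast in change, on which mediation by sleep changes depends, would be pulled toward zero in a way that is not random noise. An untreated headband or accelerometer baseline that was never recorded cannot be recreated at the analysis stage.

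**Working it through.** **The plan's own figures.** The protocol gives no figure for any sleep measure. Its sample size concerns the SDMT only: with an effect of 0.26 and SD √(1 − 0.78²) = 0.626, 80% power at two-sided 5% needs 91 per arm, 182 in total, against 184 stated. Then 184/0.9 = 204.4, rounded up to 205, against 206 stated. Both reproduce, and neither depends on the sleep recordings.

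**Step 1: overlap with treatment.** Take the Week 0 visit as the Early arm's CPAP start and count recording nights on or after it. Recording lengths come from section 7.2.5; the wear-start dates are assumed, because the protocol fixes none.

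| Wear begins | EEG nights after CPAP start (Early) | Actigraphy nights after CPAP start (Early) | Later arm |
|---|---|---|---|
| at the Week 0 visit | 3/3 | 10/10 | 0 |
| 3 nights before | 0/3 | 7/10 | 0 |
| 7 nights before | 0/3 | 3/10 | 0 |
| 10 nights before | 0/3 | 0/10 | 0 |

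The overlap thus runs from complete to nil, depending on a date that the visible text leaves open.

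**Step 2: effect on the contrast.** Let D be the true between-arm difference in a sleep measure at Week 16, with the Early arm on CPAP and the Later arm not. Let g be the share of D already present in the Early arm's baseline, with g = f × u:
- f is the share of the CPAP effect that appears in the recorded nights of someone using it;
- u is the share of Early participants using it on those nights.

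Both are assumptions. For u, 0.62 (section 5.3) and 0.70 (section 9.2) are the protocol's overall adherence figures. They serve only as anchors and are not estimates of first-night use.

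Change score: D − gD = D(1 − g). Fraction of D retained:

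| u | f = 0.25 | f = 0.5 | f = 1 |
|---|---|---|---|
| 0.50 | 0.875 | 0.75 | 0.50 |
| 0.62 | 0.845 | 0.69 | 0.38 |
| 0.70 | 0.825 | 0.65 | 0.30 |
| 1.00 | 0.75 | 0.50 | 0.00 |

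Week 16 value adjusted for baseline, with within-person correlation r and equal variances: D − r·gD = D(1 − rg). At g = 1 the retained fraction is 0.50, 0.30 and 0.20 for r = 0.5, 0.7 and 0.8. At g = 0.5 it is 0.75, 0.65 and 0.60.

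Week 16 value with no baseline term: D is retained in full.

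**Step 3: the Week 16 row.** Appendix B labels the Week 16 wearables as on CPAP, in the same row as the Later group's first mask fitting. If the Later group records before fitting, the label is wrong for that group. If it records afterwards, both arms are on CPAP and D as defined above is not observed at Week 16 either. The row does not say which applies.

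**The case against.** The strongest reply is that an untreated baseline was intended and may well be what happens. Appendix B attaches the on-CPAP label to the wearables at Weeks 16 and 32 but not at Week 0. The accelerometer is mailed and taught remotely, so it could be worn before the visit. Section 12.5 mentions wearable sensors as part of home screening, and section 4.3 uses that term for all three devices. In the copy reviewed, only the heading of Appendix A (Schedule of Events) is visible, so its content may settle the order.

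This stands as evidence of intent, and it rules out the reading that the Early arm's baseline *is* recorded on treatment: no passage says so. It does not remove the gap. No visible text dates the mailing or says that the headband is mailed, the screening row names only the Apnealink, and the label is not a reliable guide because of the Week 16 row.

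A second reply is that the damage can be limited. A randomized comparison of Week 16 values needs no baseline to be unbiased, section 9.4 does not itself require a change score, and the PSG before randomization gives untreated staging in both arms. This also stands, so a reader should not infer that later data cannot help. There are two limits. The PSG is a single laboratory night on a different device. The Week 16 comparison works only if the Later group's recording precedes its own CPAP start, which the schedule leaves unclear.

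Three further inferences go beyond the documents. That all 103 Early participants are affected assumes universal use from the first night. That the contrast is wiped out needs f = u = 1 and a change score. That the actigraphy-based activity covariate in the non-ITT models becomes post-treatment assumes a time point that section 9.4 does not give.

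**Conclusion.** The point holds as a scheduling gap: following the Week 0 row as written gives a baseline partly or wholly on CPAP in one randomized arm, and nothing visible prevents it. Overlap ranges from 0/3 to 3/3 EEG nights and from 0/10 to 10/10 actigraphy nights. The resulting attenuation cannot be fixed from the protocol. For the values of f and u tabulated, a change score keeps between 87.5% and 0% of the true difference when all recorded nights follow CPAP start. Loss at the severe end requires CPAP to act fully and be used by everyone at once.

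The exposure is confined to secondary objective 4 and the exploratory mediation analysis. The SDMT primary analysis, the sample size and the oximetry baseline from the screening Apnealink are unaffected. This is a cheap improvement worth making before more baselines are collected; it does not threaten the trial's main result.

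**What to change.** - In Appendix B, move the headband EEG and actigraphy from the Week 0 row to a new entry after PSG-confirmed eligibility and before the Week 0 visit. The remote set-up that section 7.2.5 describes for the accelerometer can be used for both devices.
- In section 7.2.5, state that the 3 EEG nights and 10 actigraphy days must be complete before the first CPAP night, in both arms.
- Reconcile the Week 16 row, so that the Later group's recording has a stated position relative to its own CPAP start and the on-CPAP label says which group it applies to. Check Appendix A for agreement.

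The cost is an amendment to two schedule rows and one sentence, with the same devices and the same number of nights. The downside is up to about 10 days between confirmed eligibility and Week 0.

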5.6 Randomization and Blinding

Participants will be randomized 1:1 to one of the following groups:

Early CPAP group: Brain Health Support PRO sleep modules (BHP-sleep; a web-based sleep education platform) and Continuous Positive Airway Pressure (CPAP) for 8 months; or

Later CPAP group: BHP-sleep for first 4 months, then BHP-sleep and CPAP for remaining 4 months of participation.

From the beginning of month 5 until the end of month 8, both groups will be receiving CPAP.

Randomization will be performed using an instance of the OxMAR software package hosted on a Sunnybrook Research Institute computer. Randomization will be carried out in blocks of 2 and stratified such that equal numbers from each recruitment type (i.e. clinic, community) will be in each group.

Research personnel not involved in assessments or interventions will access the randomization list to allocate participants in each group. Personnel performing outcome assessments and methodologists performing analyses will be blinded to group allocation. Randomization will be completed by a dedicated analyst, who will distribute randomization codes (using a random number generator) to determine the treatment arm to which each participant is allocated. Assessors and Research Assistants administering the interventions will be blinded and as such, only the analyst overseeing randomization will have access to the password-protected randomization list.

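### The Week 16 sleep recordings are listed as on CPAP with no arm label and no order relative to the Later group's first fitting, so control-arm 4-month recordings could be made on treatment

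*Protocol*

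**What the plan says.** Appendix B lists for the Week 16 visit: "CPAP mask fitting + teaching (later CPAP group) - MRI - Sleep wearables on CPAP: Apnealink, MUSE-EEG, Actigraphy". The recordings carry no arm label. At Week 32 the wording is the same, "ADAS-Cog) - Sleep wearables on CPAP: Apnealink, MUSE-EEG, Actigraphy". At Week 0 the on-CPAP qualifier is absent: "CPAP mask fitting + teaching (early CPAP group) - MRI Sleep wearables: MUSE-EEG, Actigraphy".

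The support calls do name an arm. For the Early group they run "Week 0 days 1, 2, 5, 7; weeks 1, 2, 3, 4, 6, 8, 10, 12, 16 (early CPAP group", and for the Later group "Week 16 days 1, 2, 5, 7; weeks 17, 18, 19, 20, 22, 24, 28, 32 (later CPAP group", so Later-group support begins the day after the Week 16 visit.

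Three sections fix when the Later group is treated. Section 4.1: "Participants randomized to this group will start BHP-sleep without CPAP for first 4 months". Section 5.6: "From the beginning of month 5 until the end of month 8, both groups will be receiving CPAP". Section 6.1: "At the start of the 5th month, participants in the Later CPAP group will receive a study-provided auto-tiltrating CPAP device".

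Section 7.2.5 schedules 1 night of Apnealink, 3 nights of home EEG and 10 days of wrist accelerometry at 16 weeks (4 months) for all participants. It does not say whether these are on or off CPAP, or before or after a fitting. Section 3.2 makes the sleep features that mediate the CPAP effect on cognition a secondary objective (number 4). Section 9.4 treats the mediation analysis as exploratory, with slow wave sleep percentage as the primary mediator.

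**The concern.** Week 16 is the only point at which randomization compares CPAP with no CPAP. By Week 32 both arms are treated and differ only in duration. To show that a change in sleep carries the effect of CPAP on the SDMT, the control arm's sleep must be recorded untreated at Week 16, and preferably before the SDMT that it is meant to explain.

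As written, the schedule can be followed so that neither holds. Staff who apply the Week 16 line to everyone, or who start the devices at the visit, would record the Later group during its first nights on CPAP. The device logs in section 7.2.6 would show which recordings were affected. They cannot supply the untreated recording that was not made, and dropping the affected participants would break the randomized comparison and could introduce selection.

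**Working it through.** **The plan's own figure.** No figure in the protocol rests on this point. The nearest is the sample size in section 9.2. With residual SD √(1 − 0.78²) = 0.626 and a difference of 0.26, the noncentral t calculation gives 80.04% power at N = 184, as stated. That calculation concerns the SDMT and does not use the sleep recordings.

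**Step 1: labels in Appendix B after randomization.**

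| Item | Arm named |
|---|---|
| Week 0 mask fitting | Early |
| Weeks 0–16 support calls | Early |
| Week 16 mask fitting | Later |
| Week 16 recordings, on CPAP | none |
| Weeks 16–32 support calls | Later |
| Week 32 recordings, on CPAP | none |

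The two unlabelled CPAP items share their wording. At Week 32 no label is needed, because both arms are treated. At Week 16 the arms differ, and the same wording no longer says who is recorded in what state.

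**Step 2: can the recordings fit inside the visit?** No. The visit lasts 2–3 hours, and the recordings need 1 night, 3 nights and 10 days. They must fall before or after it.

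**Step 3: the two possibilities for the Later group.**
- *Before the visit:* the group has not been fitted, so the recordings are untreated and precede the 4-month SDMT. The on-CPAP qualifier then cannot apply to this arm.
- *After the visit:* the group has been fitted and its support calls start on day 1. The recordings are on CPAP to whatever extent the device is used, and they follow the SDMT.

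No visible text chooses between these.

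**Step 4: size.** Let a be the arm difference in a sleep measure at Week 16 when the Later group is recorded untreated. Let f be the share of Later participants recorded on CPAP, and k the effect of the first nights as a fraction of the four-month effect. With equal CPAP use in the two arms, the Later mean moves by f·k·a towards the Early mean, so

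contrast = a − f·k·a = a(1 − f·k).

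The remaining share does not depend on a. The documents give neither f nor k. For assumed k from 0.25 to 1:

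| f | k = 1 | k = 0.25 |
|---|---|---|
| 0.25 | 1 − 0.25 = 75% | 1 − 0.0625 = 94% |
| 0.5 | 1 − 0.5 = 50% | 1 − 0.125 = 88% |
| 1 | 1 − 1 = 0% | 1 − 0.25 = 75% |

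**The case against.** The strongest reply is that the Later group arrives at Week 16 untreated, so the qualifier naturally covers only those already using CPAP. The accelerometer is mailed and explained by videoconference (section 7.2.5), so recording need not start at the visit. Nor does position in the table show order, since MRI is also listed after mask fitting. Appendix A, the schedule of events, is present only as a heading in the text at hand and may state the order. All of this stands. It makes the benign reading plausible, but no visible sentence states it.

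The labelling argument is also only suggestive. Week 32 is a second unlabelled CPAP item, so the table does not label every one.

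A reader might infer that Appendix B contradicts sections 4.1, 5.6 and 6.1. It does not strictly do so: recordings begun after the Week 16 fitting would fall in month 5, when those sections have the Later group on CPAP. Nor is the 4-month comparison in section 9.4 contradicted. It concerns the SDMT and then the plasma and MRI outcomes, all listed at the Week 16 visit without the qualifier.

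A reader might also want a figure for lost power. The documents do not support one. The effect on sleep measures, f and k would all have to be assumed, and power for an arm difference in a mediator is not power for a mediation effect. Section 9.4 also does not state the mediator's time point or whether exposure is assigned arm or actual use, so the reliance on the Week 16 contrast is an inference from objective 4 and the design.

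**Conclusion.** The point holds as an ambiguity with a real consequence, limited in scope. Followed as written, Appendix B allows the control arm's 4-month sleep recordings to be made on CPAP and after the SDMT. The randomized Week 16 contrast in sleep physiology would then keep a share 1 − f·k: anything from nearly all of it to none, depending on two quantities that the protocol does not give. The formula assumes equal CPAP use in both arms, and the ranges assume k between 0.25 and 1.

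The damage is confined to secondary objective 4 and its exploratory mediation analyses. The SDMT, plasma and MRI comparisons stand. The conclusion is provisional on Appendix A, which may already fix the order. It still merits correction before Week 16 visits accumulate, because an untreated 4-month recording cannot be made once CPAP has begun.

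**What to change.** Reconcile Appendix B with section 7.2.5 and check that Appendix A agrees. At Week 16, apply the on-CPAP qualifier to the Early group only. State that the Later group's Week 16 recordings are completed before its CPAP fitting. This leaves the time at which CPAP starts unchanged and also puts that group's mediator before its 4-month SDMT.

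The cost is scheduling. The recordings take 10 days if run together, or 10 + 3 + 1 = 14 days in sequence, and must be arranged before the Week 16 visit. The protocol describes mailing for the accelerometer and for the Apnealink at screening, but not for the EEG headband, which would have to reach participants earlier. No procedure is added.

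For Week 0, the order of EEG and actigraphy relative to the Early group's fitting is likewise unstated, and its support calls begin on day 1. Those entries should be reconciled; no particular order is proposed here.
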